2.1 OBJECTIVES AND SCIENTIFIC AIMS

Primary Aim:

- To conduct a randomized controlled trial comparing the efficacy of Individual Meaning-Centered Psychotherapy (IMCP), a standardized Individual Supportive Psychotherapy (ISP) and Enhanced Usual Care (EUC) in improving meaning and spiritual well-being and overall quality of life and reducing psychological distress (depression and anxiety, hopelessness and desire for hastened death) in a sample of patients with advanced cancer.

Secondary Aims:

- To examine clinical and demographic variables that may correspond to differential responses to Individual Meaning-Centered Psychotherapy (e.g., potential moderating influences such as gender, race/ethnicity, religiosity, level of pre-intervention social support, optimism, physical symptom burden, prognostic awareness, and treatment dose).
- To assess the relative impact of Individual Meaning-Centered Psychotherapy on different aspects of meaning (e.g., purpose, coherence, existential vacuum), as well as on different aspects of spiritual well-being (meaning versus faith),
- To explore whether an enhanced sense of meaning —explains|| (mediates) improved psychological well-being (i.e., increased quality of life, decreased psychological distress).

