Specifically, meaning is viewed as both an intermediary outcome, as well as a mediator of changes in these important psychosocial outcomes. Religious faith is not expected to directly impact psychosocial outcomes, but may moderate the intermediary outcome of meaning (see, for example, Nelson et al., 2002, indicating that religious faith does not provide a unique contribution to enhanced psychosocial outcomes after controlling for spirituality). This model also presumes that other factors will impact response to a meaning-based intervention, including prognostic awareness, psychosocial treatment preference, and therapeutic alliance. We recognize that the directionality of many of the variables included in this model could potentially be bi-directional; however, we are presenting the model we believe underlies the intervention.

Figure 2: Study Model – Mediators and Moderators of Treatment Outcome

Spiritual Well-Being/meaning and Its Impact on Psychosocial Outcomes in Advanced Cancer

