5. Duke-UNC Functional Social Support Questionnaire (FSSQ): As a measure of perceived social support we are utilizing an 11-item multidimensional, functional social support questionnaire (range 0-4). (Broadhead et al., 1988). The Duke-UNC is a reliable and valid self-report instrument that generates a total score representing overall social support, and two subscale scores corresponding to confidant support and affective support. This measure has adequate demonstrated levels of internal consistency and test-test reliability ($> .60$), as well as significant correlations with other measures of social functioning. (5 minutes; T1)
6. Life Orientation Test Revised (LOT-R): This 8-item measure of optimism has been widely used in studies of adjustment to stress and illness and depression (range 8-56). Studies have demonstrated high levels of reliability (e.g., alpha coefficients ranging from =.76-.80 and test-retest reliability of .79) as well as concurrent and discriminant validity (Scheier & Carver, 1985). While most studies have treated the LOT-R as a trait-like measure (dispositional optimism), Carver et al. (1993) found that LOT-R scores were influenced by situational stress in a sample of women with breast cancer. (2 minutes; T1)

Measures of Psychotherapy Preference, Process and Adherence:

1. Pre-Randomization Preference Questionnaire (PRP): A face valid questionnaire developed by the investigators to assess patients' preference for interest in participating in a psychotherapy intervention, and preferences regarding content and group assignment. Patients are asked to rate (on a 0-4 Likert-type scale) their preferences for 3 aspects of psychotherapy content: a) social support, b) expression of feelings, c) finding a sense of meaning and purpose in life. Patients are also being asked to indicate their preference for the meaning-centered vs. supportive psychotherapy vs. enhanced

usual care study arms (they are told that this information is solely for analytic purposes and will not influence group assignment). (1 minute; PR)

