Output:	Noncentrality parameter λ	= 20.8000000
	Critical F	= 2.9936309
	Sample size	= 104
	Actual power	= 0.8062691
	Pillai V	= 0.1666667

A sample size of 104 per randomization arm (138 at baseline) at post-intervention would accommodate a post-intervention attrition rate of up to 25%, which is within the attrition rate in our pilot IMCP trial. The estimated sample size at the follow-up time point (week 15) is 90 participants per intervention condition.

Based on our current IMCP Group psychotherapy intervention, we are currently recruiting at a rate of 5 – 6 individuals to participate. This study involves the IMCP individual therapy, which is more flexible in terms of enrolling patients quickly and scheduling for starting of the therapy sessions. Thus we are confident that we will be able to recruit at a rate of 8 – 9 individuals per month and complete the total enrollment of 414 within the 4-year recruitment period.

Data analytic plans for the secondary aims

To examine clinical and demographic variables that may correspond to differential responses to Individual Meaning-Centered Psychotherapy (e.g., potential moderating influences such as gender, race/ethnicity, religiosity, level of pre-intervention social support, optimism, physical symptom burden, prognostic awareness, and treatment dose).

We anticipate that several socio-demographic and clinical variables will moderate the impact of IMCP. For example, we expect that level of religiosity (based on the IE-12) at the baseline/pre-intervention assessment will be inversely related to treatment response (i.e., less religious individuals will be more likely to experience benefits from this intervention than more religious individuals). We also predict that level of social support will moderate improvement, with those patients reporting higher levels of social support receiving the greatest benefits (because of the emphasis on connectedness to others as a source of meaning in the IMCP intervention). On the other hand, we expect that patients with poorer physical functioning (e.g., lower Karnofsky score), greater pain severity and overall symptom burden (MSAS Global Distress Index scores) will be less likely to benefit from the interventions, in part because unmanaged physical symptoms may impede participation.

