Analyses: Putative explanatory covariates will be identified and tested statistically using the method originally described by Baron and Kenny (1986), and more recently by MacKinnon (2008). Specifically, these will involve Multi-Variate Analysis of Covariance (MANCOVA) using the changes in the six primary outcomes (post intervention minus baseline) as a function of intervention condition, controlling as covariates the effects of gender, race/ethnicity, and baseline covariates in religiosity, social support, optimism, physical symptom burden, pain severity, and overall symptom burden. This analytic approach entails the following advantages: 1) change scores have the advantage of clearly identifiable direction of change, 2) psychosocial outcomes are measured on an interval scale (such as measures of temperature in the Fahrenheit or Celsius scales), so that change scores are less prone to problems associated with respondents using different internal psychological scales; and 3) precedence exists (Flay et al. 1995) in interventions designed for behavioral change. This method offers several advantages, both in terms of power as well as interpretation, to a traditional repeated measures design for analyzing data when both independent and dependent variables are assessed at two or more time points (Huck & McLean, 1975; Willet, 1988-9). Change score analyses will include the baseline score as a covariate if change is significantly correlated with baseline score (as is often the case).

To assess the relative impact of Individual Meaning-Centered Psychotherapy on different aspects of meaning (e.g., purpose, coherence, existential vacuum), as well as on different aspects of spiritual well-being (meaning versus faith):

Two additional MANOVA models will be carried out. In the first model, pre-post change scores of different aspects of meaning (e.g., purpose, coherence, existential vacuum) will be modeled by intervention conditions to examine the relative impact of IMCP on these outcomes. The canonical weights will be used to estimate the relative contribution of each mean components on the overall canonical function. Components of spiritual well-being will also be analyzed similarly, in a separate MANOVA model. Univariate ANOVA contrasts will be used to compare IMCP against ISP and IMCP against EUC.

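### The secondary moderator aim names prognostic awareness, but the only specified analysis omits it and contains no arm-by-moderator term, so it cannot estimate differential response for any moderator

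*Combined protocol and SAP*

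**What the plan says.** All references are to the combined protocol and SAP.

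- **The aim (Section 2.1, restated in Section 11.0 under the secondary aims).** It sets out to examine variables linked to differential response to IMCP: "potential moderating influences such as gender, race/ethnicity, religiosity, level of pre-intervention social support, optimism, physical symptom burden, prognostic awareness, and treatment dose".
- **The conceptual model (Section 3.0).** It presumes that "other factors will impact response to a meaning-based intervention, including prognostic awareness, psychosocial treatment preference, and therapeutic alliance".
- **The directional hypotheses (Section 11.0).** Besides religiosity and social support, they predict that patients with "lower Karnofsky score), greater pain severity and overall symptom burden (MSAS Global Distress Index scores) will be less likely to benefit".
- **The analysis (Section 11.0, Analyses).** Changes in the six primary outcomes are modelled "as a function of intervention condition, controlling as covariates the effects of gender", followed by a list that carries no wording to mark it as examples: "effects of gender, race/ethnicity, and baseline covariates in religiosity, social support, optimism, physical symptom burden, pain severity, and overall symptom burden".
- **Data collection (Sections 4.2 and 7.1).** Prognostic awareness is assessed at T1 and T3 by patient self-report plus a therapist rating. Arm preference is recorded before randomization ("Patients are also being asked to indicate their preference for the meaning-centered vs. supportive psychotherapy vs. enhanced" usual care), and patients are told that it serves analysis only.

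**The concern.** The aim asks whether the effect of IMCP differs between kinds of patient. A statistician who follows Section 11.0 literally meets two obstacles. Prognostic awareness, which the aim names, is not in the model. And the model only adjusts for the variables that it does contain, so it returns one arm effect averaged over them and nothing on how that effect varies.

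At stake is a stated secondary aim. If moderator terms are devised only once the data are in hand, both the choice of moderators and the form of the model become post hoc. Prognostic awareness is also costly to leave without a stated analysis. Section 7.1 collects it from patients, from therapists and, for a subset, from about 50 oncologists.

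**Working it through.** The plan gives no figure for this analysis, so the check is a comparison of the lists, then of the model form, then of precision.

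**1. The lists side by side**

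| Variable | Aim (2.1, 11.0) | Conceptual model (3.0) | Hypotheses (11.0) | Analysis model (11.0) |
|---|---|---|---|---|
| Gender | yes | – | – | yes |
| Race/ethnicity | yes | – | – | yes |
| Religiosity | yes | – | yes | yes |
| Social support | yes | – | yes | yes |
| Optimism | yes | – | – | yes |
| Physical symptom burden | yes | – | – | yes |
| Prognostic awareness | yes | yes | – | **no** |
| Treatment dose | yes | – | – | **no** |
| Karnofsky | – | – | yes | **no** |
| Treatment preference | – | yes | – | **no** |
| Therapeutic alliance | – | yes | – | **no** |
| Pain severity | – | – | yes | yes |
| Overall symptom burden | – | – | yes | yes |

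(The conceptual-model column covers the sentence quoted from Section 3.0. Figure 2 is not reproduced in the text.) The aim and the model share six variables. The aim has two that the model lacks (prognostic awareness, dose), and the model has two that the aim lacks (pain severity, overall symptom burden).

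**2. Which missing variables could be baseline moderators**

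- *Prognostic awareness:* yes, using the T1 self-report part. EUC patients have no study therapist, so the therapist rating cannot serve a three-arm model. Sections 4.2 and 7.1 place T1 after patients learn their arm, so the measure is pre-intervention but not pre-disclosure. The same caveat applies to religiosity, social support, optimism and the MSAS, all taken at T1.
- *Karnofsky:* yes. It is recorded at T0 and used for stratification (Section 12.3).
- *Treatment preference:* yes. It is recorded before randomization.
- *Dose and alliance:* no. Both arise after randomization. EUC has no sessions, and the alliance measure is not given in that arm.

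**3. What the model form can deliver**

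The stated form is: change = arm + covariates. Differential response requires: change = arm + moderator + arm × moderator.

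An illustrative two-arm simulation shows the gap (n = 20,000; standard normal moderator; true arm effect 0.20; true interaction 0.30; no moderator effect in the comparator arm).

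- Covariate-only model: arm 0.180, moderator 0.150. It has no term for the interaction. The 0.150 is the average of slopes 0 and 0.30 in the two arms.
- Model with the interaction term: arm 0.182, moderator −0.006, interaction 0.305.

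Adding prognostic awareness to the covariate list would therefore not answer the aim.

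**4. Precision of the repaired analysis**

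Inputs: 104 per arm at post-intervention (Section 11.0); one outcome with SD 1 (assumed); a binary moderator with fraction p at one level (assumed 0.5 or 0.3).

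The standard error of the difference between two subgroup IMCP-ISP effects is √[2 × (1/(104p) + 1/(104(1−p)))].

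- p = 0.5: √[2 × (1/52 + 1/52)] = √0.0769 = 0.277
- p = 0.3: √[2 × (1/31.2 + 1/72.8)] = √0.0916 = 0.303

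The detectable interaction (80% power, two-sided 5%) is (1.96 + 0.84) × SE = 2.80 × SE.

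- p = 0.5: 2.80 × 0.277 = 0.78 SD
- p = 0.3: 2.80 × 0.303 = 0.85 SD

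A multi-level variable does worse. With three equal preference levels (assumed), each cell holds 104/3 = 34.7. Comparing two levels gives √(4/34.7) = 0.340, and 2.80 × 0.340 = 0.95 SD.

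**The case against.** **The aim's list is only illustrative.** It is worded as examples, and the analysis paragraph opens by saying that putative covariates will be identified and tested. This stands in part: the aim does not bind the sponsor to a fixed set. It does not explain why a variable that the aim names is absent from the one model then spelled out. Open wording also leaves the choice until after the data are seen.

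**The interaction is implied.** The paragraph cites a methods paper whose title concerns moderators and mediators. But the sentence that turns the citation into a model describes covariate control and stops there.

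**Power is poor, so little is lost.** The detectable interactions are indeed large. That supports an exploratory label. It does not support leaving the aim without an estimator.

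**A stronger reading to resist.** A reader might infer that prognostic awareness and treatment preference are both required moderators, and that their absence from the covariate list is why the plan gives no answer on them. The documents do not support this. Preference appears in neither statement of the aim. It is named in the Section 3.0 background model, which specifies no analysis, so leaving it out contradicts no stated objective. Nor is absence from the list the main cause: gender, religiosity and social support are on it and still get no test of differential response. Nor should all the lists simply be merged, since that would bring dose and alliance in as if they were baseline variables.

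**Conclusion.** The point holds for prognostic awareness and for the form of the model. The stated aim names prognostic awareness, the analysis omits it, and with no arm-by-moderator term the plan cannot estimate differential response for it or for any of the eight listed variables. Karnofsky, which the hypotheses say will affect benefit, is also missing. Preference is a gap between data collected and analyses planned, and conflicts with no stated aim.

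The primary MANOVA is untouched. The loss is confined to a secondary aim, and the repaired analysis could detect only large interactions: about 0.78 to 0.85 SD for a binary moderator, more for a multi-level one. These figures assume 104 analysed per arm, one outcome with unit SD, and splits between 50/50 and 30/70. The textual finding depends on none of them. The plan should be corrected, but the matter does not threaten the trial's main conclusion.

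**What to change.** 1. Use one list of pre-intervention moderators in Section 2.1 and in both places in Section 11.0. Keep the eight listed variables; add the T1 self-reported prognostic awareness measure and baseline Karnofsky.
2. Fix the scoring of the self-report prognostic measure in advance, since Section 7.1 describes a combination of three approaches. Use the self-report part only, and state that T1 follows disclosure of assignment.
3. For each moderator, fit an arm-by-moderator term. Report the IMCP-ISP and IMCP-EUC differences by level with confidence intervals, labelled exploratory.
4. Optionally, treat pre-randomization arm preference in the same way, stating that it lies outside the stated aim.
5. Take treatment dose out of the baseline moderator list. Say separately how dose and therapeutic alliance will be examined, given that both arise after randomization and have no counterpart in EUC.

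The cost is SAP wording and some extra exploratory models on data already scheduled for collection. The downside is a somewhat larger family of exploratory tests with wide intervals: ten moderators in place of eight, or eleven with preference.

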1. **Sociodemographic Questionnaire:** Sociodemographic information will be obtained at the pre-randomization time point consisting of questions concerning age, gender, ethnicity, education, employment history, marital status and household composition, and religious affiliation and practices. Significant medical and other life events which occur during the course of treatment and follow-up will be recorded for each patient. (5 minutes; T0)
2. **Distress Thermometer (DT):** The Distress Thermometer (Roth et al., 1998) is a single-item visual analog scale used to screen cancer patients for the presence of psychological distress with a 0-10 range. The National Cancer Center Network (NCCN) Clinical Practice Guidelines for Distress Management recommend use of the DT, along with a 34-item problem checklist (NCCN, 2003, 2009). An extensive research literature has documented the utility of the DT as a screening tool for oncology settings, and has identified a cut-off of 4 or greater for identifying clinically significant psychological distress (e.g., Grassi et al., 2009; Jacobsen et al., 2005). (2 minutes; T0, T2, T3)
3. **Karnofsky Performance Rating Scale (KPRS):** Observer-rated scale used by physicians to report patient's level of physical performance with a range of 0-100. (Karnofsky & Buchenal, 1949; Coscarelli-Schag, 1984). KPRS is rated upon admission screening and at each assessment. (1 minute; T0, T3, T4)

Health Status Measures:

1. Health Status Interview (HS): Extent of disease, degree of medical co-morbidity, concomitant therapies, and significant medical events occurring during the study will be recorded for each patient. (5 minutes; T1)

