4. Physician Prognostic Awareness Questionnaire (8 items; See Appx S): When feasible, a subset of participants' oncologists (approximately 50) will be asked to complete a brief, face valid questionnaire, developed in collaboration with Fordham University. The questionnaire consists of 8 items assessing physicians' perceptions of the discussion about prognosis with their patients, including the patient's understanding of their prognosis and any potential barriers to their understanding. (5 minutes; T1)
5. Health Status and Outcome (Appendix T): HIS charts will be reviewed at the end of study or after death notification for the following information: DNR, hospitalization within one month of death, hospital death. (Chart Review; T4 and post-death)

Measures of Meaning:

1. Life Attitude Profile-Revised (LAP-R): The LAP-R is a 48-item self-report multidimensional measure of discovered meaning and purpose in life and the motivation to find meaning and purpose in life based on Frankl's work (Reker, 1992). Items are rated on a 7-point Likert-type scale of agreement. The LAP-R evaluates 6 dimensions: purpose, coherence, life control, death acceptance, existential vacuum, and

goal seeking, which are used to calculate two composite subscales: the Personal Meaning Index (having life goals and a sense of direction) and Existential Transcendence (degree to which meaning and purpose has been discovered) (range 8-56). The LAP-R has high internal consistency (Cronbach's alpha coefficients ranging from 0.77 to 0.91; Reker, 1992). (5 minutes; T1, T2, T3, T4)

2. Unfinished Business Questionnaire (UBQ): This 3-item measure asks participants to identify any matters in their lives (e.g., relationships, work) perceived as unfinished or unresolved (range 0-10). Participants who endorse —unfinished business— are asked to provide a troubling example and to rate their distress related to this example. (under 5 minutes; T1, T3, T4)

Measures of Spiritual Well-Being:

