2. Schedule of Attitudes towards Hastened Death (SAHD): This 20-item questionnaire (range 0-20) was developed by the responsible investigators as a self-report measure of interest in hastened death ([name], [name], et al., 1999; 2000). This measure has been administered to more than 300 patients with terminal cancer and HIV/AIDS, and has demonstrated high levels of reliability (alpha coefficient=.88 and median item-total

correlation=.43). In addition, the SAHD has demonstrated concurrent validity, correlating 0.88 with the clinician-rated Desire for Death Rating Scale (Chochinov et al., 1995), and somewhat more modestly ($r=.47$ to 0.65) with measures of depression and overall psychological distress. This range of scores and pattern of correlations with measure of depression is consistent with previous research (e.g., Chochinov et al., 1995; [name] et al., 2001). (under 5 minutes; T1, T2, T3, T4)

3. Hopelessness Assessment in Illness (HAI): The Hopelessness Assessment in Illness scale (HAI) is a brief, 8-item questionnaire specifically developed through a R01-funded research study ([name], P.I.; [name], Co-P.I.) to assess hopelessness in cancer patients with advanced disease and terminal illness (range 0-16). ([name] et al., in press). The HAI has demonstrated a high degree of internal consistency (coefficient alpha above .80) and construct validity (e.g., a correlation of .74 with clinical ratings of hopelessness). The HAI demonstrated incremental validity over and above existing measures of hopelessness, such as the Beck Hopelessness Scale, which our group has used in previous research studies. (under 5 minutes; T1, T2, T3, T4)
4. McGill Quality of Life Questionnaire (MQOL): A brief, self-report instrument designed to assess various domains of psychological, spiritual, and physical functioning among terminally ill patients (Cohen et al., 1995). Patients rate their current functioning on a scale of 0 to 10. The physical and psychological domains of the MQOL are highly correlated with other measures of quality of life, although the existential/spiritual domain assessed by this measure has not typically been included in other quality of life measures. This measure has demonstrated reliability (internal consistency $> .70$ for the subscales), and adequate levels of concurrent validity (e.g., correlation of .34 with the Spitzer Quality of Life Index) (under 5 minutes; T1, T2, T3, T4)

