To explore whether an enhanced sense of meaning —explains (mediates) improved psychological well-being (i.e., increased quality of life, decreased psychological distress):

This mediation analysis will be carried out using a MANCOVA model. The dependent variables will be the changes in psychosocial outcomes at the follow-up assessment time point (week 15 minus baseline) in quality of life and psychological distress as a function of intervention condition, adjusting for the post-intervention change in meaning (post-intervention LAP-R minus baseline LAP-R). Thus, the follow-up outcomes will be predicted by enhanced sense of post-intervention meaning. This lagged analysis is necessary because there is a potential confounding effect, for example, in using the post-intervention changes in meaning in predicting post-intervention quality of life. The lagged analysis between follow-up outcomes in quality of life and psychological distress and post-intervention changes in meaning preserves a plausible temporal ordering of causes and effects.

Intent-to-treat analyses and handling of missing data:

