Intent-to-treat (ITT) analysis is the gold standard in evaluating the relative efficacy of therapeutic regimes for patients assigned to different treatment arms whether or not they comply with the full treatment plan as defined in the protocol. In contrast to studies that assess clinical outcomes that are observable whether or not patients comply with therapy, it is likely in this study that patients who fail to participate in particular counseling sessions will also be missing the corresponding outcome data. Thus, examination and imputation of incomplete data will be an integral part of our ITT analysis. Data for intermediate time points might be imputable by one of several available statistical techniques. However, it is more problematic to assess outcomes for patients who essentially drop out of the study, namely, who are missing the final (and possibly preceding) evaluations. Although we shall endeavor to obtain final evaluation-time data even for patients who discontinue the counseling, but because of the likelihood that premature withdrawal is related to deteriorating physical health, we cannot rely on this and will therefore use appropriate statistical methods. One preferred approach is the Pattern-Mixture Model (Hedeker & Gibbons, 1997), which assumes that patients can be grouped into a small number of implicit cohorts with different patterns of missing data. This method models the trajectories of responses within each cohort and combines results across cohorts to make overall comparisons between treatment arms. The Pattern-Mixture Model can be relatively easily applied in practice using a publicly accessible SAS macro. This approach will handle two potential, inter-related issues, namely, intent-to-treat analysis and missing data while making a global assessment of the overall efficacy of the two types of counseling. We anticipate that the majority of patients will complete most or all of the planned sessions and the corresponding assessments. However, our pilot data suggest that there may be sufficient attrition to warrant use of the above-described approach even if drop-out rates do not differ significantly between the two treatment arms.

Missing data:

Because attrition may significantly impact the MANOVA, we will utilize several techniques for dealing with missing data (Nich & Carroll, 1997; Singer & Willett, 1991). These techniques may

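### The mediation model omits physical decline between baseline and T3, so decline that lowers both meaning and later quality of life can be read as mediation by meaning

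*Combined protocol and SAP*

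**What the plan says.** The mediation paragraph of section 11.0 specifies one MANCOVA. On the outcome side, "The dependent variables will be the changes in psychosocial outcomes at the follow-up assessment time point (week 15 minus baseline"), covering quality of life and psychological distress. On the predictor side, these are modelled "as a function of intervention condition, adjusting for the post-intervention change in meaning (post-intervention LAP-R minus baseline LAP-R"). No clinical covariate is named.

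The plan recognises that confounding is possible and answers it with timing: "This lagged analysis is necessary because there is a potential confounding effect", the example being T3 meaning used to predict T3 quality of life. The claim made for the lag is that it keeps a plausible order of cause and effect.

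Elsewhere in the document:

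- The moderator analysis (section 11.0) does adjust, "controlling as covariates the effects of gender, race/ethnicity, and baseline covariates in religiosity, social support, optimism, physical symptom burden", but at baseline only. It also adds an outcome's own baseline score when that score correlates with change.
- The intent-to-treat text (section 11.0) plans for dropout "because of the likelihood that premature withdrawal is related to deteriorating physical health".
- MQOL, an outcome in this model, is described in section 7.1 as "designed to assess various domains of psychological, spiritual, and physical functioning among terminally ill patients".
- Section 7.1 schedules the physical measures. For Karnofsky: "KPRS is rated upon admission screening and at each assessment. (1 minute; T0, T3, T4"). The MSAS, which has a physical symptom distress subscale, is taken at T1, T3 and T4. LAP-R is taken at all four of T1 to T4.

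**The concern.** Arm is randomized; change in meaning is not. The coefficient on LAP-R change therefore has the standing of an observational association, and it is causal only if the common causes of meaning change and later outcome are controlled. In advanced cancer the obvious candidate is physical deterioration. A patient who declines between baseline and T3 may lose meaning by T3 and have worse quality of life at T4 even if meaning has no influence on quality of life. The document itself expects such decline, and one of its outcome scales includes physical functioning.

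The lag guards against reversed direction. It does not remove a cause already acting before T3 that continues to T4. In addition, the outcome is change from baseline to T4, so it contains the interval over which LAP-R change is measured.

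What is at stake is the mechanism claim. Section 3.0 presents enhanced meaning as the catalyst for the other benefits, and this is the one planned analysis that tests that model. The plan states no indirect-effect estimate or test, so a significant LAP-R term is what is likely to be read as mediation.

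**Working it through.** **Inputs.** The plan expects 90 patients per arm at week 15 (section 11.0), so n = 3 × 90 = 270. It gives no power figure or significance level for the mediation analysis; the 0.01 level belongs to the primary MANOVA. I use two-sided 0.05 and one outcome at a time. The documents give no correlations, so every q and r below is an assumption.

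**Step 1: what the planned model estimates.** Let decline from baseline to T3 correlate q with LAP-R change and r with baseline-to-T4 outcome change within arm (absolute values), and let meaning have no effect. With variables standardized within arm, the expected LAP-R coefficient is q × r instead of 0. The model has an intercept, two arm indicators and LAP-R change, leaving 266 degrees of freedom, and the t statistic has noncentrality

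δ = qr / √(1 − (qr)²) × √266.

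| q | r | qr | δ | P(LAP-R p<0.05), formula | Simulation |
|---|---|---|---|---|---|
| 0.09 | 0.19 | 0.017 | 0.28 | 6% | 5–7% |
| 0.18 | 0.37 | 0.067 | 1.09 | 19% | 19–20% |
| 0.26 | 0.46 | 0.120 | 1.96 | 50% | 50–52% |
| 0.33 | 0.54 | 0.178 | 2.95 | 84% | 85–86% |

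The simulation sets baseline physical status at variance 1, T3 status at baseline plus noise of SD 0.8, and T4 status at T3 plus half of the earlier change plus noise of SD 0.48. LAP-R and outcome load on status at 0.1/0.15, 0.2/0.3, 0.3/0.4 and 0.4/0.5, with residual change variance 0.8. With equal correlations, the formula gives 5% at 0.1, 10% at 0.2, 31% at 0.3 and 75% at 0.4.

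**Step 2: when this becomes a false two-path finding.** Mediation of a treatment effect also needs the arm to change meaning. In the 0.26/0.46 setting:

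- If therapy does not change LAP-R, both paths are significant in about 0.05 × 0.50 = 2.5% of trials. Across all four settings the simulation gives 0–4%.
- If IMCP raises LAP-R by 0.4 in simulation units: the SD of LAP-R change is √(0.3² × 0.64 + 0.8) = 0.926, so the shift is 0.4/0.926 = 0.43 SD. Against one comparator, δ = 0.43 × √(90/2) = 2.88, a power of 82%. Both paths are then significant in about 0.82 × 0.50 = 41% (simulation 41–42%).

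**Step 3: what adjustment achieves (0.26/0.46 setting).** Baseline physical status alone does nothing: the rate stays at 50%. Carrying over the moderator analysis's baseline covariates would therefore not be enough.

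Adding baseline and T3 status helps, but measurement error leaves a remainder. At single-visit reliability 0.8, the error variance of the change is 0.25 × (1 + 1.64) = 0.66, so the reliability R of the change is 0.64/(0.64 + 0.66) = 0.49. The remaining partial correlation is

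qr(1 − R) / √((1 − q²R)(1 − r²R)) = 0.065,

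which gives 19% (simulation 17–18%). At reliability 0.9, R = 0.69, the partial correlation is 0.042 and the rate is 10% (simulation 10%).

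**The case against.** A reader might infer that decline will be reported as mediation, or that a significant LAP-R term is what decline alone should produce. The documents do not support that. They give no correlation of decline with LAP-R change or with outcome change. At correlations of 0.1 to 0.2 the distortion is small, and if the therapy does not move LAP-R a two-path finding stays rare. This objection stands, and it limits the point to what the model can do.

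The plan can also be defended on its wording. It offers the lag for one stated example and claims only plausible ordering. Its baseline-score rule, written under the moderator aim, might extend to this model, so it may be less bare than it looks. Both are fair. Neither reaches decline during the mediator window: the rule would add the outcome's own baseline, and Step 3 shows that even baseline physical status leaves the rate unchanged. The missing-data methods deal with absent values, not with confounding among patients who are observed.

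The strongest objection is to a simple remedy. The pilot in section 3.0 reports that IMCP reduced symptom distress relative to massage (MSAS-GDI, b = 0.42, p = .0003). T3 symptom distress may therefore be affected by treatment, and adjusting for it could hide real mediation. This also stands. It rules out requiring the LAP-R term to survive adjustment before mediation is claimed, but it does not justify reporting only the unadjusted model.

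Finally, the aim is secondary and exploratory, and the physical measures will be collected anyway. That limits the severity. It does not remove the value of fixing the versions before the results are seen.

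**Conclusion.** The concern holds as a possibility whose size is unknown. The planned model contains only arm and LAP-R change, the lag does not remove a persisting common cause, and nothing else in the plan covers physical decline between baseline and T3. With no true effect of meaning, the LAP-R term would be significant in about 6% to 50% of trials as the assumed correlations move from 0.09/0.19 to 0.26/0.46, and more often above that. A false two-path finding is likely mainly if IMCP does raise LAP-R, which is what the trial hopes to show. These figures rest on one outcome, a two-sided 0.05 level, 270 patients, decline that persists after T3, and correlations that are all assumed. The primary MANOVA and the randomized comparisons are unaffected.

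**What to change.** In the mediation paragraph of section 11.0, keep the planned model and prespecify beside it:

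- (a) a version adding Karnofsky at T0 and T3 and the baseline covariates already listed for the moderator analysis;
- (b) a version also adding the MSAS Physical Symptom Distress subscale at T1 and T3.

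Report the LAP-R coefficient with its confidence interval from all three. Add a sensitivity analysis for residual mediator-outcome confounding, for example the product qr that would bring the coefficient to zero. Describe the path from meaning to outcome as observational. Do not use survival after adjustment as a pass/fail rule.

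The cost is a few sentences and some extra model runs, with no new data and no added patient burden. The downside should be stated in the plan: because T3 physical status may itself respond to treatment, the adjusted arm coefficient is not the full direct effect and the adjusted LAP-R coefficient may be conservative. Version (a), which uses an observer-rated T3 measure, is there to show how much depends on the self-reported symptoms added in (b).
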